5.3 Safety Endpoint-related Definitions

Treatment-Emergent Adverse Event (TEAE)

TEAE is defined as adverse events starting on or after first dose of tarlatamab as determined by "Did event start before first dose of investigational product" equal to "No" or missing on the Events eCRF, and up to and including 65 days after the last dose of tarlatamab excluding the events reported after End of Study date. Events that are directly related to lung cancer or disease progression (including, but not limited to, preferred terms "Small cell lung cancer", "Disease progression" etc.) will be excluded from TEAE analysis.

Treatment-related Adverse Event (TRAE)

TRAE is defined as TEAE with the relationship flag on the Events eCRF indicating there is a reasonable possibility that the event may have been caused by tarlatamab. Event with missing relationship with tarlatamab is assumed to be treatment-related.

6. Analysis Sets

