8.4.6.1 Time Period and Frequency for Collecting and Reporting Safety Event Information

8.4.6.1.1 Adverse Events

The adverse event grading scale to be used for this study will be the CTCAE v5.0 and is described in Section [11.4](#), with the following exceptions: CRS and ICANS will be graded according to American Society for Transplantation and Cellular Therapy (Lee et al, 2019) as described in [Table 6-2](#). Tumor lysis syndrome will be graded based on CTCAE v5.0 but will be managed based on Cairo Bishop criteria (Coiffier et al, 2008).

The investigator is responsible for ensuring that all adverse events observed by the investigator or reported by the subject that occur after first dose of investigational product(s) or noninvestigational product(s)/auxiliary medicinal product(s) through the

SFU visit **or 60 days after the last dose of the study treatment, whichever is later**, are reported using the Events CRF.

Disease progression is an efficacy endpoint. Disease progression of SCLC is not considered an adverse event and should not be reported as an adverse event **unless there is evidence as suggesting a causal relationship between the investigational product(s) and/or noninvestigational product(s)/auxiliary medicinal product(s) and progression or symptom/sign of progression of the SCLC** as indicated in Section 11.4. Progression of the subject's underlying malignancy will be recorded in the Tumor Response CRF page as part of efficacy data collection and not on the Events CRF.

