8.4.6.1.2 Serious Adverse Events

The investigator is responsible for ensuring that all serious adverse events observed by the investigator or reported by the subject that occur after signing of the informed consent through the SFU visit **or 60 days after the last dose of study treatment, whichever is later**, are recorded in the subject's medical record and are submitted to Amgen or its designee using the Events CRF.

Disease progression and death due to disease progression of SCLC are not considered serious adverse events and will not be reported as serious adverse event **unless there is evidence as suggesting a causal relationship between the investigational product(s) and/or noninvestigational product(s)/auxiliary medicinal product(s) and progression or symptom/sign of progression of the SCLC** as indicated in Section 11.4. Progression of the subject's underlying malignancy will be recorded in the Tumor Response CRF page as part of efficacy data collection and not on the Events CRF. Death due to disease progression is to be recorded in the End of Study CRF page and not on the Events CRF.

All serious adverse events will be collected, recorded, and reported to the sponsor or designee immediately and no later than 24 hours of the investigator's awareness of the event, as indicated in Section 11.4. The investigator will submit any updated serious adverse event data to the sponsor immediately and no later than 24 hours of it being available.

Since the criteria of the CTCAE grading scale differs from the regulatory criteria for serious adverse events, if adverse events correspond to grade 4 CTCAE toxicity grading scale criteria (eg, laboratory abnormality reported as grade 4 without manifestation of

life-threatening status), it will be left to the investigator's judgment to also report these abnormalities as serious adverse events. For any adverse event that applies to this situation, comprehensive documentation of the event's severity must be recorded in the subject medical records.

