Both Amgen and the investigator reserve the right to terminate the investigator's participation in the study according to the Clinical Trial Agreement. The investigator is to notify the external review body in writing of the study's completion or early termination and send a copy of the notification to Amgen.

Subjects may be eligible for continued treatment with Amgen investigational product(s) by a separate protocol or as provided for by the local country's regulatory mechanism. However, Amgen reserves the unilateral right, at its sole discretion, to determine whether to supply Amgen investigational product(s) and by what mechanism, after termination of the study and before the product(s) is/are available commercially.

Compensation

Any arrangements for compensation to subjects for injury or illness that arises in the study are described in the Compensation for Injury section of the Informed Consent that is available as a separate document.

11.4 Appendix 4. Safety Events: Definitions and Procedures for Recording, Evaluating, Follow-up and Reporting

Definition of Adverse Event

Adverse Event Definition

 An adverse event is any untoward medical occurrence in a clinical study subject irrespective of a causal relationship with the study treatment. Note: An adverse event can therefore be any unfavorable and unintended sign (including an abnormal laboratory finding), symptom, or disease (new or exacerbated) temporally associated with the use of a treatment, combination product, medical device, or procedure. Note: Treatment-emergent adverse events will be defined in the Statistical Analysis Plan.
Events Meeting the Adverse Event Definition

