- When an adverse event or serious adverse event occurs, it is the responsibility of the investigator to review all documentation (eg, hospital progress notes, laboratory, and diagnostics reports) related to the event.
- The investigator will then record all relevant adverse event/serious adverse event information in the Events CRF.
- The investigator must assign the following mandatory adverse event attributes:
 - Adverse event diagnosis or syndrome(s), if known (if not known, signs or symptoms)
 - Dates of onset and resolution (if resolved)
 - Did the event start before first dose of investigational product
 - Assessment of seriousness
 - Severity (or toxicity defined below)
 - Assessment of relatedness to investigational product(s), noninvestigational product(s)/auxiliary medicinal product(s)
 - Assessment of relatedness to study-required activity and/or procedures is only required for Serious Adverse Events
 - Action taken
 - Outcome of event
- It is not acceptable for the investigator to send photocopies of the subject's medical records to sponsor in lieu of completion of the Events CRF.
- If specifically requested, the investigator may need to provide additional follow-up information, such as discharge summaries, medical records, or extracts from the medical records. In this case, all subject identifiers, except for the subject number, will be blinded on the copies of the medical records before submission to Amgen.
- The investigator will attempt to establish a diagnosis of the event based on signs, symptoms, and/or other clinical information. In such cases, the diagnosis (not the individual signs/symptoms) will be documented as the adverse event/serious adverse event.

Evaluating Adverse Events and Serious Adverse Events

Assessment of Severity

The investigator will assess severity for each adverse event and serious adverse event reported during the study. The assessment of severity will be based on:

The Common Terminology Criteria for Adverse Events (CTCAE), version 5.0 which is available at the following location:

http://ctep.cancer.gov/protocolDevelopment/electronic_applications/ctc.htm.

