- The investigator may change their opinion of causality in light of follow-up information and send a serious adverse event follow-up report with the updated causality assessment. In this case, for sites reporting serious adverse events via EDC, the investigator or sub-investigator must reconfirm causality in the EDC system within 72 hours of the serious adverse event being entered on the Events CRF.
- The causality assessment is 1 of the criteria used when determining regulatory reporting requirements.

Follow-up of Adverse Event and Serious Adverse Event

- The investigator is obligated to perform or arrange for the conduct of supplemental measurements and/or evaluations as medically indicated or as requested by Amgen to elucidate the nature and/or causality of the adverse event or serious adverse event as fully as possible. This may include additional laboratory tests or investigations, histopathological examinations, or consultation with other healthcare professionals.
- If a subject is permanently withdrawn from investigational product(s) and/or noninvestigational product(s)/auxiliary medicinal product(s) because of a serious adverse event, this information must be submitted to Amgen.
- If a subject dies during participation in the study or during a recognized follow-up period, the investigator will provide Amgen with a copy of any postmortem findings including histopathology.
- New or updated information will be recorded in the originally completed Events CRF.
- The investigator will submit any updated serious adverse event data to Amgen immediately and no later than 24 hours of receipt of the information.

Reporting of Serious Adverse Event

Serious Adverse Event Reporting via Electronic Data Collection Tool

- The primary mechanism for reporting serious adverse event will be the EDC system.
- If the EDC system is unavailable, then the site will report the information to Amgen using a paper-based Serious Adverse Event Contingency Report Form (also referred to as the eSAE Contingency Report Form) (see [Figure 11-1](#)) immediately and no later than 24 hours of the investigator's awareness of the event.

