11.11.1 Specific Guidance for Cytokine Release Syndrome

Cytokine release syndrome (CRS) is defined as a supraphysiologic response following any immune therapy that results in the activation or engagement of endogenous or infused T-cells and/or other immune effector cells. Symptoms can be progressive, must include fever at the onset, and may include hypotension, capillary leak (hypoxia) and end organ dysfunction.

Clinical signs and symptoms of CRS are non-specific and may include a combination of the following:

- constitutional: fever \pm rigors, malaise, fatigue, anorexia, myalgias, arthralgias, nausea, vomiting, headache
- skin: rash
- gastrointestinal: nausea, vomiting, diarrhea
- respiratory: tachypnea, hypoxemia
- cardiovascular: tachycardia, widened pulse pressure, hypotension, increased cardiac output (early), potentially diminished cardiac output (late)
- coagulation: elevated D-dimer, hypofibrinogenemia \pm bleeding
- renal: azotemia
- hepatic: transaminitis, hyperbilirubinemia

The symptoms associated with the CRS event do not meet the definition of an adverse event as defined in Section 11.4. Therefore, the CRS associated event (ie, CRS, cytokine storm) should be documented on the Events electronic eCRF as the diagnosis. However, since it is important to document all symptoms related to a CRS event, a CRS Symptoms eCRF will also be available to record the symptoms associated with each CRS event.

If the severity of a CRS event changes from the date of onset to the date of resolution, record a single event for each increased level of severity on the Events eCRF and fill out an associated CRS Symptoms eCRF. If the symptoms worsen enough to impact the overall CRS grade, it is important to remember to record a new CRS event on the Events eCRF with the appropriate grade.

Temperature may normalize within a few hours of treatment, whereas the other components of CRS take longer to resolve. Once such therapies are used, the patient is

considered to still have CRS, even in the absence of fever, until all signs and symptoms leading to the diagnosis of CRS have resolved. Likewise, CRS can be downgraded in an afebrile patient treated with anticytokine therapy as their hemodynamic status and/or hypoxia improves. Typically, a patient with severe CRS in whom fever, oxygen, and pressor requirements have resolved may be assumed to have resolved CRS unless there are alternative causes for the fever, hypoxia, and/or hypotension.

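### The TEAE definition has no clause for worsening, so a serious event that begins before dosing and becomes worse or fatal on tarlatamab can drop out of the TEAE-based adverse event tables

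*SAP*

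**What the plan says.** The protocol leaves the definition to the SAP. Its adverse event appendix (Protocol 11.4) states that "Treatment-emergent adverse events will be defined in the Statistical Analysis Plan". SAP 5.3 then reads: "TEAE is defined as adverse events starting on or after first dose of tarlatamab as determined by" the Events eCRF question on pre-dose onset. A record qualifies when that question is answered No or left blank and the event falls within 65 days after the last dose. Treatment-related events are defined as a subset of TEAEs.

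Four other provisions decide what happens to an event that is already open at the first dose:

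- Protocol 8.4.6.1.2 collects serious adverse events "that occur after signing of the informed consent through the SFU visit", or to 60 days after the last dose if that is later. Screening SAEs are therefore on the Events CRF.
- Protocol 11.4 makes the onset question, "Did the event start before first dose of investigational product", a mandatory attribute of each event.
- Protocol 11.4, under follow-up of events, says: "New or updated information will be recorded in the originally completed Events CRF".
- Protocol 11.11.1 tells sites to "record a single event for each increased level of severity on the Events eCRF" when severity rises, but only for cytokine release syndrome.

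SAP 9.6.2 builds its adverse event incidence summaries, including those for events of interest, on treatment-emergent events. SAP 2.1 names TEAE incidence as the safety and tolerability endpoint.

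**The concern.** A treatment-emergent definition should capture harm that appears or gets worse on treatment. This one captures only new onset. Suppose an SAE begins in screening, is still ongoing at cycle 1 day 1, and then rises in grade or becomes fatal. If the site updates the existing record, the answer on pre-dose onset remains Yes and the event is not a TEAE, whatever its later grade or outcome.

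The study has one arm and about 30 subjects, so the absolute incidences are the safety result and no comparator would reveal a missing event. A fatal or serious on-treatment worsening could be absent from the tables where a reader would look for it.

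**Working it through.** **The plan's own safety figure.** SAP 3.2 gives a 79% to 96% probability of seeing at least one event in 30 subjects at true rates of 5% to 10%. The formula is 1 − (1 − p)^30.

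- p = 0.05: 1 − 0.95^30 = 0.7854, or 79%.
- p = 0.10: 1 − 0.90^30 = 0.9576, or 96%.

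Both reproduce. The figure is not in dispute, but it applies only to events that the definition counts.

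**Tracing one event through the text.** Take an acute SAE that starts in the screening window of up to 21 days, is ongoing at the first dose, and increases in grade afterwards.

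1. It is on the Events CRF, because SAE collection starts at consent (Protocol 8.4.6.1.2).
2. Its mandatory onset attribute is Yes (Protocol 11.4).
3. The higher grade or fatal outcome is updated information, which 11.4 directs to the original record. The rule for a new record at each grade increase covers CRS only.
4. SAP 5.3 requires No or a blank, so the event is not a TEAE. It is not a treatment-related event either, because that set lies within the TEAEs.
5. It is therefore absent from the SAP 9.6.2 tables of all, serious, grade 3 or higher, fatal and related events, and of events leading to withdrawal, interruption or reduction.

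**What still shows it.** Laboratory shift tables run from baseline to worst on-study grade (SAP 9.6.4). Vital signs (9.6.5), reasons for discontinuation (9.2) and overall survival (5.2) do not use the TEAE definition. A death or discontinuation would appear there, but not as a fatal or serious adverse event with a preferred term.

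**Size of one case (n = 30, exact Clopper-Pearson 95% interval).**

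| Fatal TEAE table | Incidence | 95% CI |
|---|---|---|
| Event not counted, 0/30 | 0% | 0 to 11.6% |
| Event counted, 1/30 | 3.3% | 0.1 to 17.2% |

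**Chance of at least one case.** The documents give no rate for dosed subjects with a pre-dose SAE that later worsens. Let q be that rate, as an assumption. The chance is 1 − (1 − q)^30 and the expected number is 30q.

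| Assumed q | Expected subjects | Chance of at least one |
|---|---|---|
| 0.5% | 0.15 | 14% |
| 1% | 0.30 | 26% |
| 2% | 0.60 | 45% |
| 5% | 1.50 | 79% |

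The eligibility rules favour the low end of this range.

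**The case against.** The strongest reply is that the protocol already treats worsening as an adverse event. Protocol 11.4 counts the exacerbation of a chronic or intermittent pre-existing condition. It also excludes ordinary fluctuations of conditions present at study start only if they do not worsen. Medical history is collected through the first dose (Protocol 8.2.3), so a screening illness may be documented as pre-existing. A site could then enter the worsening as a new event with post-dose onset, and SAP 5.3 would count it. The instruction to update the original record is a general follow-up bullet and does not expressly address post-dose worsening. This stands in part: omission is possible, not certain. However, the exacerbation wording does not plainly reach an acute SAE already on the Events CRF, so the result depends on how each site reads the instructions.

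The second reply is rarity, and it stands. Exclusion 211 removes acute or uncontrolled systemic infection within 7 days of the first dose, exclusion 229 removes other clinically significant conditions judged to pose a risk, and ECOG 0 to 1 is required.

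A reader might also infer three stronger points that the documents do not support:

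- **That every safety output loses the event.** Laboratory shifts, vital signs, disposition and overall survival do not depend on the TEAE definition.
- **That every record predating tarlatamab is serious.** Protocol 8.4.6.1.1 collects non-serious events from the first dose of investigational or noninvestigational product. Dexamethasone is given within 1 hour before tarlatamab on cycle 1 day 1 (6.1.2.1), so a non-serious event in that interval is also recorded. This leaves the gap open.
- **That counting a blank onset answer as treatment-emergent is an error.** The field is mandatory, so blanks should be few, and the default errs towards counting events against the drug.

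**Conclusion.** The gap is real but narrow. SAP 5.3 has no worsening clause, no protocol text supplies one, and a pre-dose SAE that worsens or becomes fatal on tarlatamab can be missing from all TEAE-based adverse event tables. This rests on one reading that the documents favour but do not compel: that the site updates the existing record and does not open a new one.

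One case moves an incidence by 1/30, or 3.3 points, and could turn a fatal TEAE count of one into zero. How often this would happen cannot be taken from the documents; the rates above are assumptions. The primary endpoint, ORR, is unaffected. The definition should be corrected before database lock because TEAE incidence is the stated safety endpoint and the change is small.

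**What to change.** In SAP 5.3, extend the definition to include events that start before the first dose of tarlatamab and increase in grade, or become fatal, on or after the first dose and up to 65 days after the last dose. Keep the existing exclusions for disease progression and for events reported after the end of study.

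The clause works only if the worsening is dated. CRF completion guidance should therefore require its date and grade, for example through a new Events record, as is already done for CRS. That guidance must be worded consistently with the Protocol 11.4 instruction on updates; if a new record is chosen, a short clarification of 11.4 may be needed. A new record with post-dose onset would already qualify under the current rule, so the SAP clause mainly protects against worsening entered as an update. Counting by subject avoids double counting within a preferred term.

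The cost is one SAP sentence, brief site guidance and a little data entry. A reported incidence may become slightly less favourable.

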6.1.6 Excluded Treatments, Medical Devices, and/or Procedures During Study Period

The following treatments and/or procedures are excluded within the timeframes specified during the study:

- Other investigational agents, devices (other than those specified in the protocol) and procedures are prohibited while on study treatment.
- Anticancer therapies other than those specified in the protocol are prohibited while on study treatment.
- Radiation therapy
 - Exception: Radiation therapy for symptom control (eg, bone metastasis) or brain metastasis treatment may be allowed after discussion with the medical monitor. The radiation therapy should not include the thoracic field and must have been completed at least 7 days before the subsequent dose of tarlatamab.
- Immunosuppressive agents with the exception of those required by protocol, treatment for adverse events, CNS metastases, corticosteroid replacement therapy, or unless agreed upon by the investigator and medical monitor.
- During tarlatamab treatment: Live and live-attenuated vaccines are prohibited for the duration of tarlatamab treatment.
 - Live viral non-replicating vaccine (eg, Jynneos for mpox infection) is allowed when administered > 3 days before or > 3 days after a tarlatamab infusion.
 - Seasonal influenza vaccines for injection are generally killed virus vaccines and are allowed when administered > 3 days before or > 3 days after a tarlatamab infusion. However, intranasal influenza vaccines (eg, Flu - Mist®) are live-attenuated vaccines, and are not allowed at any time during tarlatamab treatment.
 - Vaccinations for coronavirus disease 2019 ([COVID-19], severe acute respiratory syndrome coronavirus 2 [SARS-CoV-2] vaccination) are generally not live or live-attenuated and are allowed when administered > 3 days before or > 3 days after a tarlatamab infusion.
 - After completion of tarlatamab treatment: live and live-attenuated vaccines are prohibited for a further **60** (+5) days after the last dose of tarlatamab.
- Subjects must not schedule any major elective surgery during the treatment period and for at least 30 days after the last administration of study treatment. If a subject undergoes any unexpected surgery during the course of the study, all study

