8.1.3 End of Treatment

Upon permanent discontinuation from study treatment for any reason, an end of treatment visit will be performed at the time the decision is made to discontinue study treatment (preferably within 14 days after last dose of study treatment) and prior to the start of subsequent anti-cancer therapy.

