5.2 Efficacy Endpoint-related Definitions

Best Overall Response (BOR)

The subject's best response assignment depends on the findings of both target and non-target disease and also takes into consideration the appearance of new lesions and confirmation of response based on the findings from MRI/CT scans. Confirmation of progressive disease is not required. BOR is based on all post-baseline disease assessments that occur prior to the initiation of subsequent anticancer treatment. At least 5 weeks from the first dose of IP must elapse without radiological disease progression to meet the minimum criteria for SD duration in order to assign a BOR of SD. In general, subjects not classifiable under the RECIST 1.1 response categories due to inadequate data or early death are classified as not evaluable (NE) for BOR but will be counted in the denominator of all response rate calculations. BOR per RECIST 1.1 has the following possible categories: complete response (CR), partial response (PR), stable disease (SD), progressive disease (PD), not evaluable (NE). The rules for deriving the BOR are detailed in Appendix B.

Objective Response (OR)

OR is defined as a BOR of CR or PR per RECIST 1.1. Subject without a post-baseline tumor assessment is considered non-responder.

Objective Response Rate (ORR)

ORR is defined as proportion of subjects with BOR of CR or PR per RECIST 1.1.

Disease Control (DC)

DC is defined as a BOR of CR or PR or SD per RECIST 1.1.

Disease Control Rate (DCR)

DCR is defined as proportion of subjects with a BOR of CR or PR or SD per RECIST 1.1.

Duration of Disease Control (DoDC)

DoDC is defined as time from **the date of first dose of tarlatamab** until the first documentation of disease progression or death due to any cause, whichever occurs first. Only subjects with a BOR of confirmed response (CR/PR) or SD are evaluated for DoDC.

DoDC (Months) = (earlier of progressive disease date or death date – **date of first dose of tarlatamab** + 1) × 12 / 365.25

DoDC is censored following the same censoring rules as PFS ([Appendix C](#)).

Duration of Response (DOR)

DOR is defined as time from first documentation of CR or PR per RECIST 1.1 until the first documentation of progressive disease or death due to any cause, whichever occurs first. Only subjects who with a BOR of confirmed response (CR/PR) are evaluated for DOR.

DOR (Months) = (earlier of progressive disease date or death date – response start date + 1) × 12 / 365.25

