9.6.2 Adverse Events

The Medical Dictionary for Regulatory Activities (MedDRA) version 27.0 or later is used to code all events categorized as adverse events to a system organ class and a preferred term.

The subject incidence of adverse events will be summarized for all TEAEs, TRAEs, serious TEAEs, grade 3 or higher TEAEs, fatal TEAEs, TEAEs leading to withdrawal of tarlatamab, TEAEs leading to interruption and/or reduction of tarlatamab. Subject incidence summary by system organ class and preferred term in descending order of frequency will be provided for all TEAEs, TRAEs, serious TEAEs, grade 3 or higher TEAEs, fatal TEAEs, TEAEs leading to withdrawal of tarlatamab, TEAEs leading to interruption and/or reduction of tarlatamab. Where appropriate the summary will also be provided by worst grade. Above summaries will not be created if two or fewer subjects experience the AE, subject-level data may be provided instead.

Severity of CRS and ICANS events will be graded using American Society for Transplantation and Cellular Therapy (ASTCT) (Lee et al, 2019) criteria. Severity of tumor lysis syndrome (TLS) will be graded using CTCAE version 5.0 but will be managed based on Cairo Bishop criteria ([Coiffier et al, 2008](#)). Severity of all other adverse events will be graded using CTCAE version 5.0.

Subject incidence of events of interest (standardized MedDRA queries and/or Amgen Medical Queries) will also be summarized according to their categories and preferred term if appropriate.

Adverse Events of Interest (EOI):

The summary of subject incidence of treatment-emergent adverse events of interest standardized MedDRA queries and/or Amgen Medical Queries such as cytokine release syndrome, hypersensitivity, immune effector cell associated neurotoxicity syndrome (ICANS) and associated neurological events, neutropenia, and neurological events will be summarized. The summary will include grade \geq 2, grade \geq 3, grade \geq 4, serious, fatal, and events leading to interruption and/or reduction and discontinuation of IP.

The subject incidence of above treatment-emergent EOIs, serious treatment-emergent EOI, grade 3 or higher treatment-emergent EOI, fatal treatment-emergent EOI, treatment-emergent EOI leading to discontinuation of investigational product and treatment-emergent EOI leading to interruption and/or reduction of

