investigational product will be tabulated by preferred term. CRS and immune-effector cell-associated neurotoxicity syndrome (ICANS) will be graded according to American Society for Transplantation and Cellular Therapy (ASTCT) ([Lee et al. 2019](#)).

The summaries of time to onset of EOI from first dose, time to onset of EOI after each dose from last prior dose, and duration of treatment-emergent EOI will be provided. Additionally, summaries of time to onset and duration of EOI will be provided for grade 2 or higher and grade 3 or higher EOIs respectively.

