Appendix C. PFS Censoring Rules

Situation up to DCO/EOS	Date of Event or Censor	Outcome
No evaluable post-baseline tumor assessments, no death recorded	Date of first dose date of IP	Censor
PD	Date of first detection of PD	Event
No PD, but death recorded	Date of death	Event
Start of new anti-cancer therapy prior to any PD or death	Date of last evaluable tumor assessment before or on start of new anti-cancer therapy	Censor
No PD, no death recorded, no start of new anti-cancer therapy	Date of last evaluable tumor assessment	Censor
Death or PD immediately after 2 or more missed tumor assessment (14 weeks)	Date of last evaluable tumor assessment prior to the first missing assessment ^a	Censor

^a This supersedes the previous rules that result in PFS event at date of PD or death.

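### The 65-day TEAE window runs past the start of later anticancer therapy; a supplementary cut version of the neutropenia summaries and the grade 3 or higher table would be a cheap improvement

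*SAP*

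**What the plan says.** **Window.** SAP 5.3 defines a TEAE as an event starting on or after first dose "and up to and including 65 days after the last dose of tarlatamab". It leaves out only events reported after the End of Study date and events directly tied to lung cancer or its progression. Later anticancer therapy is not mentioned.

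**Collection.** Protocol 8.4.6.1.1 collects adverse events through the safety follow-up visit or 60 days after last dose, whichever is later. Protocol 8.1.4 and SAP 5.1 place that visit at 60 (+5) days and hold it whether or not new therapy has begun.

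**When later therapy can start.** Protocol 6.1.6 says "Anticancer therapies other than those specified in the protocol are prohibited while on study treatment". Protocol 8.1.3 places the end-of-treatment visit "preferably within 14 days after last dose of study treatment) and prior to the start of subsequent anti-cancer therapy". After that visit, new therapy may begin while the 65-day window is still open.

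**Tables.** SAP 9.6.2 tabulates grade 3 or higher TEAEs regardless of cause. It names neutropenia among the treatment-emergent events of interest ("and associated neurological events, neutropenia, and neurological events will be summarized"). For these events it plans incidence, time to onset from first dose, and also "time to onset of EOI after each dose from last prior dose, and duration of treatment-emergent EOI will be provided". Onset and duration are repeated for grade 2 or higher and grade 3 or higher. No safety summary ends at the start of new therapy; the only sensitivity analyses (SAP Tables 9-1 and 9-2) concern efficacy.

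**The concern.** Protocol 2.3 lists neutropenia as an adverse drug reaction of tarlatamab, so its frequency, timing and duration are among the safety results readers will look at. In a single-arm study no control rate exists against which to set neutropenia caused by a later drug. If an event starts under that drug but inside the window, the all-cause summaries show it as part of tarlatamab's profile.

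The SAP already separates out later therapy for some efficacy endpoints. SAP 5.2 states that "BOR is based on all post-baseline disease assessments that occur prior to the initiation of subsequent anticancer treatment", and SAP Appendix C has a censoring row for "Start of new anti-cancer therapy prior to any PD or death". The safety section has no comparable view, not even a supplementary one.

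At stake is how clearly the neutropenia onset and duration summaries, and to a smaller degree the grade 3 or higher incidences, describe tarlatamab itself. Tables of events leading to interruption, reduction or discontinuation of tarlatamab are not at issue.

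**Working it through.** **1. The plan's own safety figure.** SAP 3.2 gives a 79% to 96% chance of seeing at least one event among 30 subjects at true rates of 5% and 10%. 1 − 0.95^30 = 78.5% and 1 − 0.90^30 = 95.8%. The figure reproduces and is not in dispute.

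**2. Overlap between the window and later therapy.** Let the end-of-treatment visit fall on day d after last dose, and assume that new therapy starts the next day. The days of the window under new therapy are 65 − d:

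- d = 1: 64 days
- d = 7: 58 days
- d = 14: 51 days

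These are upper figures for each d. A later start of therapy shortens the overlap.

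**3. Number of cases.** This cannot be derived. The documents do not say what subjects receive after tarlatamab, when it starts, how many receive it, or how often it causes neutropenia. The only later-line agent named for China is anlotinib, a kinase inhibitor (Protocol 2.2.1), and no neutropenia rate is given for it. Only per-case effects can be shown.

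**4. Incidence, per case.** One added subject, without earlier neutropenia of that grade, is 1/30 = 3.3 points. Take an assumed on-drug count of 3/30 and an assumed 0 to 3 added subjects (a range, not a forecast). Clopper-Pearson 95% intervals:

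| Subjects | Rate | 95% CI |
|---|---|---|
| 3/30 | 10.0% | 2.1 to 26.5 |
| 4/30 | 13.3% | 3.8 to 30.7 |
| 5/30 | 16.7% | 5.6 to 34.7 |
| 6/30 | 20.0% | 7.7 to 38.6 |

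The shift is 0 to 10 points, and the intervals overlap heavily.

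**5. Onset from last prior dose, per case.** Assume n on-drug events with mean onset 7 days, plus one event under later therapy at day L. The mean rises by (L − 7)/(n + 1):

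| | L = 20 | L = 40 | L = 65 |
|---|---|---|---|
| n = 3 | 13/4 = 3.3 days | 33/4 = 8.3 days | 58/4 = 14.5 days |
| n = 12 | 13/13 = 1.0 day | 33/13 = 2.5 days | 58/13 = 4.5 days |

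The median moves less: onsets of 3, 7 and 11 days have median 7, and adding 40 gives (7 + 11)/2 = 9. SAP 9.1 reports means, medians, standard deviations and ranges, so the mean and range would carry most of the distortion. All inputs in this step are assumed.

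**6. What the treatment-related tables cover.** SAP 9.6.2 tabulates TRAEs by system organ class and preferred term and, where appropriate, by worst grade. That gives a related-only reading of incidence. The SAP lists no related-only version of the event-of-interest onset or duration summaries, so the gap is largest there.

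**The case against.** The window itself is a sound, conservative choice. It follows the collection period and a follow-up visit deliberately held regardless of new therapy. A reader might infer that the TEAE definition is wrong and should be shortened. The documents do not support that: a shorter main window would discard late tarlatamab toxicity that the study is set up to collect. This objection stands in full, and the main definition should not change.

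A reader might also infer that the neutropenia rate will be materially inflated. Nothing in the documents shows this, for the reasons in step 3 of the working. The treatment-related tables also offset much of the effect on incidence. Relatedness is a mandatory attribute of every event, and Protocol 11.4 asks the investigator to weigh concomitant therapy as another cause. SAP 5.3 adds that "Event with missing relationship with tarlatamab is assumed to be treatment-related", but missing flags should be rare. What remains is that these tables rest on attribution in an open-label study and do not extend to onset or duration. When two or fewer subjects have an event, SAP 9.6.2 replaces the main adverse event summaries with subject-level data that may be provided, which helps only if it is produced.

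A third tempting inference is that a long interval from the last prior dose marks an event under later therapy. It does not. Protocol Table 6-3 provides for delays beyond 28 days, and Table 6-2 requires a delay for grade 3 or 4 neutropenia. Long intervals can therefore arise on tarlatamab alone.

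Finally, the efficacy contrast is not an inconsistency. BOR follows an estimand limited to the time before new therapy, PFS has its own censoring rules, and OS in SAP 5.2 is not cut at new therapy. The contrast shows only that the start date is already needed in the analysis.

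A cut version has a bias of its own, because it removes late tarlatamab effects. That is a reason to show both versions; it does not argue against the supplement.

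**Conclusion.** The point holds as a cheap improvement of low severity. The uncut window is a proper main definition. It also lets neutropenia that starts under later therapy enter the all-cause event-of-interest summaries and the grade 3 or higher TEAE table, and the SAP plans no view that separates such events by date. The onset-from-last-prior-dose and duration summaries are the most exposed.

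The size of the effect is unknown. Per case it is 3.3 points of incidence out of 30. For mean onset it is between 1.0 and 14.5 days over the assumed inputs; the top figure needs only three on-drug events and an event on the last possible day. No hypothesis is tested, so the impact is descriptive. It falls mainly on the final analysis, since many subjects may still be on tarlatamab at the primary analysis. The conclusion assumes that some subjects start later therapy within 65 days of their last dose and that this therapy can cause neutropenia. The documents allow the first and are silent on the second.

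**What to change.** Keep the TEAE definition and all planned tables. In SAP 9.6.2, add a supplementary version of the neutropenia event-of-interest summaries (incidence, onset, duration) and of the grade 3 or higher TEAE table. It should count events up to the earlier of 65 days after last dose or the day before subsequent anticancer therapy starts. Show it beside the uncut version.

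Footnote subjects whose therapy start date was imputed. SAP Appendix A sets a date with a missing day to the first of the month or, if the month is that of the last dose, to last dose plus 1 day. In the second case the cut removes all follow-up after the last dose for that subject.

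The cost is a few repeated tables with one date condition. Protocol Table 1-2 already collects subsequent anticancer therapy at end of treatment, safety follow-up and long-term follow-up, and its start date is already needed for BOR and PFS. The drawback is that the cut version omits late tarlatamab effects, so it must not replace the uncut tables. If few subjects are affected, the two versions will agree, which is itself useful to report.
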